Protocol ID: IRB-HSR# 21926

Date: 11/01/2019

Knee Biofeedback Rehabilitation Interface for Game-based Home Therapy ("KneeBRIGHT")

Phase II

Protocol

Osteoarthritis (OA) is the leading cause of disability in the United States. As osteoarthritis is associated with the lower limb muscle weakness, rehabilitation focused on quadriceps and other lower extremity muscle strengthening is a well-established treatment for patients with knee OA. However, patient adherence to exercise routines is low due to the lack of guidance regarding optimal protocols, and poor engagement during the repetitive routines that patients find tedious and boring.

Long-term goal of this study is to improve knee OA outcomes through effective and motivating rehabilitation exercises. The Knee Biofeedback Rehabilitation Interface for Game-based Home Therapy ("KneeBRIGHT") system combines electromyography (EMG) biofeedback with video game therapy (VGT) to provide knee OA patients with an engaging, effective tool for conducting rehabilitation exercises at home. KneeBRIGHT aims to motivate patients with knee OA to conduct regular muscle strengthening exercise through an engaging, EMG-driven video game therapy.

Participants with age from 40-75, with independent ambulation and with the diagnosis of knee OA made by x-ray and a score of at least 2 (out of 4) on the Kellgren-Lawrence OA radiographic classification system will be included in the study. Participants with psychiatric or cognitive impairment (e.g., dementia), symptomatic spine, hip, ankle, or foot disease other than OA that would interfere with assessment of the knee will be excluded. Participants with balance or vestibular disorders, peripheral neuropathy, skin conditions that prevent EMG electrode placement, prisoner, pregnant women (by report), non-English-speaking, individuals who are visually and/or hearing impaired will also be excluded.

Eligible participants will be randomized to two groups: (1) KneeBRIGHT group; (2) Standard rehabilitation group. Both groups will undergo baseline and follow up assessment to measure the patient-reported outcomes, thigh muscle strength, and balance. Participants in both groups will undergo a 12-week program including 3 exercise sessions per week that includes a combination of in-person and at home sessions (Table 1).

Table 1 Study schedule for participants visits over 12 weeks

	Visit 1 (Screening)	Visit 2 (Baseline)	Visit 3-38	Follow-up
Study Week	0	0	1-12	13
Informed Consent	x			
Review study eligibility	x	x		
Medical History	x			
Strength, Balance & Endurance testing		x		
Questionnaires		x		x
Rehabilitation Exercises			x	x

Both groups will undergo same rehabilitation protocol which will begin with sessions supervised in the clinic by the study team physical therapist and gradually home sessions will be added. Participants in KneeBRIGHT group will perform the quadriceps strengthening exercises with the video-games based activities. The EMG biofeedback units and video game w/laptop will be provided to the subjects for home use. Subjects will receive instruction on how to apply the EMG biofeedback unit and use of the video game. KneeBRIGHT Game Activities consists of an introduction of the player to the virtual world and the missions, the player customizes the personal avatar and completes a series of calibration contractions and practice exercises to gain familiarity with the game controls. Through the EMG system, a player's muscle contractions translate into physical movements of the avatar and control of vehicles within the virtual environment. Each quest-type challenge is designed to permit play in a seated, supine, supported standing, or freestanding position, based on an individual's physical status. User interactions with the game incorporate knee extension exercises and functional movements that provide optimal therapeutic benefits.

Participants in both groups will undergo combination of home and in clinic sessions. Protocol will start with six clinic visits in order to maximize familiarity with the exercise routines and equipment. Home sessions will be added after 2 weeks in rehabilitation (Table 2). The sessions will consist of warm up, strengthening, balance, precision and gentle stretching exercises. Strengthening exercises will be focused on quadriceps, hamstring, calf and gluteal muscles. Stretching exercises will be focused on quadriceps, hamstring and calf muscles. Progression will be guided by the rehabilitation principles and participants response to the exercise. The amount of these exercises will depend on how they make the subject feel. The rehabilitation program will allow the subject to increase the amount of exercise they can perform. Exercises will be limited if the subject feels discomfort. Overall, protocol will consist of 36 sessions in total, 20 in clinic sessions and 16 home-based sessions.

Table 2 Weekly schedule for patients for in clinic and home-based therapy sessions

	One Hour Exercise Sessions	
	In clinic session	Home-based session
Week 1	3	0
Week 2	3	0
Week 3	2	1
Week 4	2	1
Week 5	2	1
Week 6	2	1
Week 7	1	2
Week 8	1	2
Week 9	1	2
Week 10	1	2
Week 11	1	2
Week 12	1	2
TOTAL	20	16

Pre and post intervention outcome measures will be compared to explore the effectiveness. Technology acceptance will also be studied in patients randomized to KneeBRIGHT group.

Overall, KneeBRIGHT has the potential to significantly enhance OA rehabilitation by improving functional recovery through physical practice of specific, adaptive exercise and promoting adherence through fun games and performance feedback. Use of the KneeBRIGHT system in teletherapy may increase access to remote/underserved areas and extend the range of existing rehabilitation facilities.

Statistical analysis

Knee function assessed by composite KOOS score prior to the study will be compared to the KOOS score recorded post-intervention to test the primary hypothesis that patients conducting the KneeBRIGHT exercise will significantly improve knee function compared to the control group. Pre-intervention KOOS scores measures will be subtracted from the post-intervention scores to produce a set of delta values. These delta values will be analyzed via Analysis of Covariance (ANCOVA). A $p \leq 0.05$ decision rule will be utilized as the rejection criterion.

Questionnaire results will be used to test the hypothesis that patients using the KneeBRIGHT system demonstrate increased levels of engagement compared to those conducting a conventional exercise routine. The questionnaire scores will be tallied to produce composite scores. These composite scores will be analyzed via a linear mixed model. A $p \leq 0.05$ decision rule will be used as the null hypothesis rejection criterion.

Timing data from the home visits will be analyzed by comparing the minutes of exercise with the KneeBRIGHT system to minutes of exercise with the standard exercise regimen in the control group to

test the hypothesis that exercise duration is greater with the KneeBRIGHT system. Mean usage time on each system will be analyzed via Student's paired *t*-test, with $p \leq 0.05$ as the null hypothesis rejection criterion.

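### Thigh strength and balance are measured in both randomised arms, but the only analysis sentence that reaches them compares pre with post and names no between-arm contrast

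*Combined protocol and SAP*

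**What the plan says.** The paragraph on randomisation, before Table 1, sets up two arms and states: "Both groups will undergo baseline and follow up assessment to measure the patient-reported outcomes, thigh muscle strength, and balance". Strength and balance are therefore planned as two-arm, two-time-point measures.

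The paragraph after Table 2 then says: "Pre and post intervention outcome measures will be compared to explore the effectiveness". It gives no arm, contrast, model, covariate or significance level.

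The Statistical analysis section follows. It covers three outcomes: composite KOOS, questionnaire composites for engagement, and minutes of home exercise. Strength, balance and endurance are not named in it.

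On treatment, the text after Table 1 says "Both groups will undergo same rehabilitation protocol" and "The sessions will consist of warm up, strengthening, balance, precision and gentle stretching exercises". The stated arm difference is "Participants in KneeBRIGHT group will perform the quadriceps strengthening exercises with the video-games based activities". The opening background says that "rehabilitation focused on quadriceps and other lower extremity muscle strengthening is a well-established treatment for patients with knee OA".

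In Table 1 as extracted, the row "Strength, Balance & Endurance testing" has one mark, under Visit 2 (Baseline), and none under Follow-up.

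**The concern.** The comparator is an active treatment. By the protocol's own background, patients in the standard arm should gain strength, and the sessions in both arms include balance work. An improvement from baseline in KneeBRIGHT patients would be expected even if the game added nothing. If that improvement were reported under the word effectiveness, part or all of it could be what standard rehabilitation also gives.

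Randomisation provides the means to separate the two, on data the text already plans to collect, but the plan does not commit to using it for these outcomes. Thigh strength is also the measure closest to the exercises that the game delivers, so it is a natural place for an effectiveness claim.

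**Working it through.** There is no planned figure to reproduce: the documents give no sample size, standard deviation, effect size or correlation. The check is a reading of each analysis sentence, followed by a short identity.

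**1. Which outcome has a stated between-arm comparison?**

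- Composite KOOS: yes. The hypothesis is against the control group; change scores go into an ANCOVA.
- Engagement questionnaires: yes. The hypothesis is against conventional exercise; linear mixed model.
- Home exercise minutes: yes. KneeBRIGHT is set against the control regimen.
- Technology acceptance: not applicable. It is explicitly studied in the KneeBRIGHT arm only.
- Thigh strength and balance: none stated. Only the general pre/post sentence reaches them.

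**2. What do the arms share?** Table 2 sums to 3 + 3 + (4 × 2) + (6 × 1) = 20 clinic sessions and (4 × 1) + (6 × 2) = 16 home sessions, 36 in all. The text applies this to both arms, with strengthening and balance exercises in the sessions.

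**3. What does a pre/post change estimate?** Let g be the mean change under standard rehabilitation (programme, practice at the test, natural course) and d the effect that KneeBRIGHT adds.

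- Mean pre/post change, KneeBRIGHT arm: g + d
- Mean pre/post change, standard arm: g
- Between-arm difference: (g + d) − g = d

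Taken as an estimate of d, the KneeBRIGHT change is off by g. This is true by definition and needs no data. The size of g cannot be had from the documents. Purely to show how the identity behaves, assume g = 0.3 to 0.5 SD and d = 0: the pre/post change then averages 0.3 to 0.5 SD with no added effect at all.

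**4. Follow-up value or change score?** With the baseline value Y0 as covariate and T for arm, Y1 = a + bT + cY0 is the same model as Y1 − Y0 = a + bT + (c − 1)Y0. The arm coefficient b is identical, so either choice serves, and the second matches the plan's use of change scores for KOOS.

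**5. How precise would the contrast be?** The approximate 95% half-width, in SD units, is t × √(2(1 − ρ²)/n), with n per arm and ρ the baseline to follow-up correlation. Both inputs are assumed here.

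- n = 25, ρ = 0.9: 2.01 × √(0.38/25) = 2.01 × 0.123 = 0.25
- n = 20, ρ = 0.5: 2.03 × √(1.5/20) = 2.03 × 0.274 = 0.56

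At such sizes the contrast is exploratory.

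**6. Is there a follow-up value?** The text before Table 1 says yes for strength and balance. Table 1 as extracted says no. It does place a week 13 mark on the row "Rehabilitation Exercises", although the programme runs over weeks 1 to 12. A mark one row out of place, in the plan or in the conversion from PDF, would explain both oddities, but this cannot be settled from the text.

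**The case against.** The strongest reply is that the sentence is a one-line overview ahead of the Statistical analysis heading. The KOOS paragraph opens with similar wording, setting the score before the study against the score after it, and then gives a between-arm hypothesis and an ANCOVA. In this document, a pre/post comparison may simply be shorthand for a between-arm analysis of change. Nothing restricts the sentence to the KneeBRIGHT arm either; the authors state such a restriction in the next sentence, on technology acceptance. If both arms' changes are reported, the reader can see the standard arm's change. The sentence is also worded as exploration, with no hypothesis or significance rule attached.

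Most of this stands. A reader might infer that the plan would claim effectiveness from the KneeBRIGHT arm's change alone, with a bias that can be quantified. The documents do not support that: they propose no such estimator, and the size of g is unknown. Nor is the game's role confined to one muscle group in a way that yields a ratio, since the text also describes functional movements within the game.

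What the reply does not remove is the omission. Shorthand worked for KOOS because the contrast and model follow it. For strength and balance nothing follows, so the contrast could be chosen after the data are seen.

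**Conclusion.** The point holds in a limited form. Strength and balance are planned in both arms, have no entry in the Statistical analysis section, and are reached only by a sentence that commits to no between-arm contrast. Whether an analysis would actually mislead depends on that sentence being followed literally, which the text permits but does not require.

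No numerical size can be given from the documents. The values in steps 3 and 5 of the working are assumptions and carry no weight for severity. The outcomes concerned are exploratory. It would be wrong to infer that the trial gives up its randomised comparison more widely: KOOS, engagement and exercise time each have a stated between-arm hypothesis and are untouched by this point.

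It would also go too far to conclude from Table 1 that strength and balance are not tested at follow-up. The text says they are, and the table may be faulty as extracted. If the table were right, however, neither a pre/post nor a between-arm comparison would be possible.

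**What to change.** Add to the Statistical analysis section, in place of the general sentence: for thigh strength and balance (exploratory), effectiveness is the between-arm difference at follow-up, or in change from baseline, adjusted for the baseline value of that measure and reported with a 95% confidence interval; within-arm pre/post changes are descriptive only. Treat endurance in the same way if it is measured at follow-up.

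Reconcile Table 1 with the text on assessments: confirm whether strength, balance and endurance are tested at follow-up, and whether the week 13 mark against the exercise row is intended.

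The cost is a few lines of wording and a little more analysis, on data the text already plans to collect. If Table 1 turns out to be the actual schedule, a follow-up testing entry is needed as well. The downside is that intervals are likely to be wide if the trial is small, which the exploratory label should make plain.

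### Does the primary KOOS analysis leave baseline KOOS out of the model by working with change scores?

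*Combined protocol and SAP*

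**What the plan says.** The primary analysis takes up a few sentences of the Statistical analysis section.

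- **Comparison:** "Knee function assessed by composite KOOS score prior to the study will be compared to the KOOS score recorded post-intervention", to test whether KneeBRIGHT improves knee function more than control.
- **Dependent variable:** "Pre-intervention KOOS scores measures will be subtracted from the post-intervention scores to produce a set of delta values".
- **Model:** "These delta values will be analyzed via Analysis of Covariance (ANCOVA".
- **Decision rule:** "A $p \leq 0.05$ decision rule will be utilized as the rejection criterion".

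The section lists no covariate and gives no model equation. It also does not say that baseline KOOS is excluded.

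The baseline value should be available for everyone. The introductory text says "Both groups will undergo baseline and follow up assessment to measure the patient-reported outcomes, thigh muscle strength, and balance", and the "Questionnaires" row of Table 1 is marked at Visit 2 (baseline) and at follow-up.

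**The concern.** The only use of baseline KOOS that the plan spells out is subtraction. Subtraction fixes the slope of follow-up on baseline at 1. When the two measurements correlate imperfectly and have similar variances, the true slope is below 1, so the change score is negatively related to baseline.

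If the model held only the arm, two things would follow. The arm effect would be less precise than it could be. And if one arm happened to start with better KOOS scores, its mean change would be pulled down by regression to the mean, with nothing in the model to correct for it. Both costs would be avoidable, since the baseline score is already collected and adjusting for it uses one degree of freedom.

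**Working it through.** **Inputs.** From the document: two randomised arms, change in composite KOOS as dependent variable, ANCOVA, significance level 0.05. Not in the document: sample size, power, effect size, SD, pre-post correlation (rho), allocation ratio and sidedness. There is therefore no stated figure to reproduce. The calculations assume a two-sided test, 1:1 allocation, equal pre and post SD (set to 1) and rho from 0.3 to 0.8.

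**Step 1: does using the change score matter once baseline is in the model?** Write the follow-up model as

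post = a + b × arm + c × baseline + error.

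Subtract baseline from both sides:

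post − baseline = a + b × arm + (c − 1) × baseline + error.

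The arm coefficient b and the residuals are unchanged; only the baseline slope is relabelled. One simulated data set (60 patients, 30 per arm) bears this out:

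| Model | Arm effect | SE | p |
|---|---|---|---|
| Follow-up on arm + baseline | 6.059 | 2.831 | 0.0366 |
| Change on arm + baseline | 6.059 | 2.831 | 0.0366 |
| Change on arm only | 5.764 | 3.411 | 0.096 |

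The first two rows are the same analysis. The third is what would be run if baseline were left out.

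**Step 2: what would omission cost?**

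- Residual variance, change on arm only: 2(1 − rho).
- Residual variance, adjusted for baseline: 1 − rho².
- Ratio, adjusted to unadjusted: (1 − rho²) / [2(1 − rho)] = (1 + rho)/2.
- Power of the unadjusted analysis where the adjusted one has 80%: Φ[(1.960 + 0.842) × √((1 + rho)/2) − 1.960].

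At rho = 0.5 the ratio is 0.75, and 2.802 × 0.866 − 1.960 = 0.467, so power is about 68%. Patients per arm below are for 80% power at an assumed effect of 0.5 SD. The last column is the shift in the estimate, −(1 − rho) × 0.2, if the KneeBRIGHT arm starts 0.2 SD higher.

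| rho | Variance ratio | Power, unadjusted | n per arm, unadjusted vs adjusted | Shift (SD) |
|---|---|---|---|---|
| 0.3 | 0.65 | 61.7% | 88 vs 58 | −0.14 |
| 0.5 | 0.75 | 67.9% | 63 vs 48 | −0.10 |
| 0.7 | 0.85 | 73.3% | 38 vs 33 | −0.06 |
| 0.8 | 0.90 | 75.7% | 26 vs 23 | −0.04 |

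These costs apply only if baseline KOOS is not in the model.

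**Step 3: does the plan leave it out?** A model of change on arm alone is a two-sample comparison, not an ANCOVA. The same section asks for a t-test by name when it compares exercise time, so choosing ANCOVA for the KOOS changes points to something beyond a two-group comparison. No other covariate is proposed anywhere in the document. The reading that needs the fewest extra assumptions is change on arm plus baseline KOOS, for which the loss is zero.

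**The case for a change.** The strongest counter-argument is that the label ANCOVA does not settle the model. As worded, the text would allow change on arm plus baseline KOOS, change on arm plus age, or some other covariate. These can give different estimates and p-values, and the choice could be made after the data are seen. The simulated example shows that the choice can move a result across 0.05.

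Nor is the plan's naming of methods fully reliable: it assigns a paired t-test to exercise time in two separately randomised groups. On this view ANCOVA might be loose wording for a comparison of mean changes.

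Part of this stands. The covariate is unnamed, and adjustment for baseline KOOS is inferred, not confirmed. But a misnamed t-test for another outcome is a separate matter and does not show that baseline is left out here. To reach a real loss one must assume either a covariate that the document never mentions or a misuse of the term, and neither is shown.

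Even if baseline were omitted, the harm would be narrower than it first appears. The plan states "Eligible participants will be randomized to two groups: (1) KneeBRIGHT group; (2) Standard rehabilitation group". Under randomisation, regression to the mean is expected equally in both arms, so the change-score comparison is unbiased over repeated randomisations and keeps its type I error. Bias arises only conditional on a realised imbalance. How large an imbalance to expect cannot be judged, because no sample size is given.

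**Conclusion.** The concern does not hold as a defect in the primary analysis. The plan specifies an ANCOVA of KOOS change without naming the covariate. On the natural reading that covariate is baseline KOOS, the model is equivalent to a baseline-adjusted analysis of follow-up KOOS, and there is no loss of power and no uncorrected imbalance.

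The drop from 80% power to about 62%, 68% or 73% (rho 0.3, 0.5, 0.7) is arithmetically right, but it depends on an omission that the document does not state, as well as on assumed equal variances and an assumed rho. Even in that case the matter is one of efficiency, and the test stays valid.

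The same question cannot be carried over simply to strength, balance and endurance. Table 1 marks that testing at baseline only, while the introductory text promises follow-up of strength and balance, so it is not clear that the data for such a model would exist.

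An unnamed covariate is missing detail of a kind that the analyst fills in the obvious way. No change to the plan is called for.

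### Does naming only a linear mixed model leave the engagement test without a valid analysis?

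*Combined protocol and SAP*

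**What the plan says.** The second paragraph of the Statistical analysis section tests whether "patients using the KneeBRIGHT system demonstrate increased levels of engagement compared to those conducting a conventional exercise routine". On the data it says "The questionnaire scores will be tallied to produce composite scores", and on the method "These composite scores will be analyzed via a linear mixed model", with rejection at p ≤ 0.05. No engagement instrument, fixed or random effects, baseline handling or tested term is given. The first paragraph is fuller for the primary endpoint: it defines a KOOS change score and names ANCOVA.

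Timing has to be read from elsewhere in the document. The protocol text says "Both groups will undergo baseline and follow up assessment to measure the patient-reported outcomes". The row "Questionnaires" in Table 1 is marked at Visit 2 (Baseline) and at Follow-up (week 13), with nothing under Visits 3–38. It does not say which questionnaires are meant. The text after Table 2 adds "Pre and post intervention outcome measures will be compared to explore the effectiveness".

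**The concern.** A mixed model is normally chosen for repeated measurements. If Table 1 is taken at face value, there are at most two engagement scores per participant, and only the week 13 score can reflect experience of the assigned routine. Four analyses then seem possible:

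- (a) the week 13 scores alone;
- (b) arm-by-time, which is a comparison of changes;
- (c) the week 13 difference adjusted for baseline;
- (d) the arm main effect averaged over both visits.

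They differ in power, and (d) halves the effect because randomised arms do not differ at baseline in expectation. The rejection threshold is fixed while the test is not, so an analyst who chose after seeing the results could reject a true null more often than 5% of the time. Poor engagement is part of the trial's rationale, so the test is not trivial even though it is not primary.

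**Working it through.** **Inputs.** From the documents: two arms, a between-arm hypothesis, a threshold of 0.05, and questionnaires marked at baseline and week 13. The documents give no sample size, SD, effect, power or correlation for this test, so there is no figure of the plan's own to reproduce. Assumed: equal SDs at the two visits, 1:1 allocation, a two-sided test, normal approximation, and baseline-to-week-13 correlation ρ of 0.2, 0.5 or 0.7. As a yardstick, (a) is set to 80% power, so its expected z is 1.96 + 0.84 = 2.80.

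**Power.** Multiply 2.80 by the effect retained divided by the relative SD:

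- (b) 1/√(2(1−ρ)) = 0.791, 1.000, 1.291
- (c) 1/√(1−ρ²) = 1.021, 1.155, 1.400
- (d) 0.5/√((1+ρ)/2) = 0.645, 0.577, 0.542

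Power is Φ(2.80 × multiplier − 1.96). For example, (b) at ρ = 0.2 gives Φ(2.22 − 1.96) = 60%.

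| Reading | ρ = 0.2 | ρ = 0.5 | ρ = 0.7 |
|---|---|---|---|
| (a) week 13 alone | 80% | 80% | 80% |
| (b) arm-by-time | 60% | 80% | 95% |
| (c) baseline-adjusted | 82% | 90% | 98% |
| (d) pooled main effect | 44% | 37% | 33% |

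**Which readings does the text support?**

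- (a) is not a mixed model. With one score per participant, a participant random effect cannot be separated from residual error.
- (b) is a mixed model, and it is where the pre/post sentence after Table 2 points.
- (c) is a mixed model when fitted with both visits as outcomes and a common baseline mean.
- (d) is a term that a mixed model can contain, but nothing in the document suggests averaging a pre-treatment visit into a treatment effect.

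That leaves (b) and (c). The gap between them is 82 − 60 = 22 points at ρ = 0.2, 10 at 0.5 and 3 at 0.7 (98 − 95).

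**False positives from choosing afterwards.** Under the null, the z statistics for (b) and (c) have correlation √((1+ρ)/2) = 0.775, 0.866, 0.922. The chance that at least one exceeds 1.96 in absolute value is 8.0%, 7.3% and 6.8%. Over (a) to (c) it is 8.9%, 9.7% and 10.1%, and over all four about 12%. Each test on its own stays at 5%.

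**Is the two-visit premise secure?** Not fully. Table 1 marks strength, balance and endurance testing at baseline only, although the text says strength and balance are assessed at baseline and follow-up. It also marks rehabilitation exercises at follow-up, in week 13, after a 12-week programme. An empty cell in a generic row of that table is weak evidence that no engagement score is taken during treatment. In the other direction, if engagement with the assigned routine can be rated only after exposure, there is no baseline score. Readings (b) to (d) then do not exist, and the power spread and the inflation both disappear.

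**The case for a change.** The strongest case for a change is that it would cost only wording. The document gives the primary endpoint a defined score and a named analysis, and gives engagement no counterpart. The direction of the hypothesis is stated, but several model terms test that same hypothesis. Even without the pooled main effect, (b) and (c) can disagree in a given trial, and at low correlation the difference in power is real (60% v 82%). The multipliers do not depend on the unknown sample size.

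All of that stands as a description of missing detail, and an analysis plan that recorded the instrument and the contrast would be better documented. It does not show that anything written is wrong. Both sensible readings hold 5% when used singly, and both estimate the full week 13 difference. The inflation arises only if an analyst runs several models and reports the smallest p-value, which the plan does not propose. The wide range of power comes mainly from (d), which no part of the text supports. A recommendation to adjust for baseline would also presuppose a baseline engagement score that the document does not show exists, and fixing week 13 as the target could discard on-treatment scores if they are collected.

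**Conclusion.** No change to the plan follows. The engagement paragraph is under-specified, but it contains no erroneous rule, and a competent analyst would fit either an arm-by-time or a constrained-baseline mixed model, or a two-group comparison if there is only one score. Each is valid for the stated between-arm hypothesis.

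Between the two mixed-model readings, the power at stake is about 22, 10 and 3 percentage points at correlations of 0.2, 0.5 and 0.7. The worst-case two-sided false-positive rate from choosing between them afterwards is about 7–8% instead of 5%. These figures rest on assumed correlations, equal variances, 1:1 allocation, an 80% yardstick and exactly two scored visits, none of which the document establishes for engagement. They lapse if engagement is scored only after exposure, and would need reworking if it is also scored during treatment. The test is not the primary one, and the primary KOOS analysis is unaffected.

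### Home exercise minutes are compared between two separately randomised groups, but the plan names a paired t-test and gives no pairing rule

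*Combined protocol and SAP*

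**What the plan says.** The design text near the start of the combined protocol and SAP sets up two parallel arms: "Eligible participants will be randomized to two groups: (1) KneeBRIGHT group; (2) Standard rehabilitation group". Each arm follows one programme: "Participants in both groups will undergo a 12-week program including 3 exercise sessions per week". The game is described for one arm: "Participants in KneeBRIGHT group will perform the quadriceps strengthening exercises with the video-games based activities". The schedule, repeated in Table 2, gives each participant 16 home sessions: "Overall, protocol will consist of 36 sessions in total, 20 in clinic sessions and 16 home-based sessions".

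The third paragraph of the Statistical analysis section takes home-session timing data and defines the contrast as "comparing the minutes of exercise with the KneeBRIGHT system to minutes of exercise with the standard exercise regimen in the control group". Its purpose is to "test the hypothesis that exercise duration is greater with the KneeBRIGHT system". The test is then named: "Mean usage time on each system will be analyzed via Student's paired" t-test, rejecting at p ≤ 0.05. The unit of pairing is not given, and neither is the sidedness of the test.

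**The concern.** A paired t-test works on within-pair differences, so it needs two values from the same or deliberately matched units. Here the two sets of minutes come from different people, and no section describes a participant contributing minutes under both regimens. The test therefore does not fit the design.

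Three things follow:

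- The result cannot be reproduced from the plan, because it depends on a pairing that nobody has defined.
- If the arms finish with different numbers, a paired test must discard participants.
- An analyst who meets the problem has to choose a replacement at analysis time, possibly with the data in view.

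Exercise duration is one of three hypotheses in the statistical section. It bears on the low adherence that the protocol gives as a motivation for the trial. It is not the primary analysis, which is the ANCOVA of KOOS change.

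**Working it through.** **Step 1: design against test.** There is no planned figure to reproduce, because the documents give no sample size, power, standard deviation or loss rate for this comparison. The check is whether any section supplies a pair. Randomisation is to two groups, each with one 12-week programme. The comparator is placed in the control group. Matching, crossover and paired randomisation are not mentioned. No pair exists.

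**Step 2: participants paired arbitrarily, equal arms.** Assumptions: normal data, equal SDs, independent participants, n = 10, 20 or 30 per arm, alpha 0.05. The difference between two unrelated participants has variance 2σ². Both tests therefore have the same non-centrality, d·√(n/2), where d is the difference in SD units. The degrees of freedom fall from 2n − 2 to n − 1. Choose d so that the two-sample test has 80% two-sided power:

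| n per arm | d | df, two-sample / paired | critical t, two-sample / paired | power if paired |
|---|---|---|---|---|
| 10 | 1.325 | 18 / 9 | 2.101 / 2.262 | 75.1% |
| 20 | 0.909 | 38 / 19 | 2.024 / 2.093 | 77.9% |
| 30 | 0.736 | 58 / 29 | 2.002 / 2.045 | 78.6% |

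One-sided, 80% becomes 77.0%, 78.7% and 79.2%. Simulated type I error with a fixed pairing (100,000 null trials) is 4.99%, 5.03% and 5.04%.

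**Step 3: unequal arms.** Assume independent 10% or 20% loss in each arm, with binomial numbers remaining.

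| Starting n per arm | chance arms end unequal (10% / 20% loss) | mean number discarded |
|---|---|---|
| 10 | 0.69 / 0.78 | 1.0 / 1.4 |
| 20 | 0.79 / 0.84 | 1.5 / 2.0 |
| 30 | 0.83 / 0.87 | 1.8 / 2.5 |

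The two-sample test uses everyone: non-centrality d·√(n₁n₂/(n₁+n₂)), df n₁+n₂−2. The paired test keeps m = min(n₁, n₂) pairs: non-centrality d·√(m/2), df m−1. With 80% two-sided power for the former, the latter has 72% (10 v 9), 71% (9 v 8), 75% (19 v 17), 74% (17 v 15), 77% (28 v 26) and 76% (25 v 23). One-sided, the range is 74–78%.

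**Step 4: dependence on the pairing chosen.** Take 200 simulated data sets, scale each to a fixed two-sample p-value, and re-pair each at random 1,000 times. At a two-sample p of exactly 0.05:

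| n per arm | pairings with p ≤ 0.05 | central 95% of paired p-values |
|---|---|---|
| 10 | 34% | 0.009–0.13 |
| 20 | 39% | 0.015–0.11 |
| 30 | 41% | 0.019–0.096 |

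At a two-sample p of 0.01, 98–100% of pairings stay significant. At 0.20, at most 1.4% become so.

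**Step 5: pairing by home session.** An analyst could instead pair the two arms' mean minutes across the 16 home sessions. Assume a constant within-participant correlation ρ. The true variance of the mean difference is 2ρσ²/n + 2(1−ρ)σ²/(16n). The paired test estimates only the second term, because stable differences between people cancel out of the session-to-session variation. The ratio of true to estimated variance is 1 + 16ρ/(1−ρ), whatever n is. Type I error is the chance that |t₁₅| exceeds 2.131/√ratio:

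- ρ = 0.1: ratio 2.78, cut-off 1.279, type I error 22%
- ρ = 0.3: ratio 7.86, cut-off 0.760, type I error 46%
- ρ = 0.5: ratio 17.0, cut-off 0.517, type I error 61%

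Simulation at 10, 20 and 30 per arm agrees.

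**Step 6: the replacement.** In 20,000 null trials at each of 10, 20 and 30 per arm (16 sessions, minutes capped at 60, assumed mean adherence 70%), pooled and Welch tests on one mean per participant had type I error of 4.7–5.2%. This held whether missed sessions counted as zero or were left out.

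**The case against.** The strongest reply is that this is a slip of wording: the author meant unpaired, an ordinary two-sample test would be run, and nothing would be lost. Even if participants were paired arbitrarily, the cost at 20 to 30 per arm is only 1.4 to 2.1 points of power, on a non-primary endpoint. The larger losses arise only if an analyst really discards participants to make pairs. Every size above also rests on an assumed sample size and loss rate.

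Most of that is fair as a statement of scale, and it is why the point is not graded higher. It does not remove the error, since the plan specifies a test that does not fit its own design. The reading that leaves the word intact and can be run, pairing by session, is much more damaging than pairing participants.

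A second reply is that the documents never say outright that nobody exercises under both regimens. Both arms share a rehabilitation protocol, and the game is tied to the quadriceps work, so KneeBRIGHT participants may also do exercises without the game. That is correct, but it does not rescue the test: the stated comparator is the control group's minutes, not a KneeBRIGHT participant's own non-game minutes.

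Finally, the documents do not say when the analysis would be done, so a choice made with the data in view is a possibility, not a prediction.

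**Conclusion.** The concern holds. The named test contradicts the parallel-group design, and this follows from the text alone with no assumption. The practical effect depends on how the wording is acted on. With participants paired blind to the data it is modest: type I error near 5%, and two-sided power of 75.1–78.6% (equal arms) or about 71–77% (unequal arms) in place of 80%. The conclusion then depends on the pairing mainly when the two-sample p-value is close to 0.05. With session-level pairing, type I error would be about 22–61%. These sizes assume normal data, 10 to 30 per arm, 10–20% loss and within-participant correlations of 0.1 to 0.5, none of which the documents give. The analysis is not primary, so the error should be corrected but does not threaten the trial's main conclusion.

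**What to change.** Required: in the third paragraph of the Statistical analysis section, replace the paired t-test with an independent two-sample t-test (or a linear model with an arm term) on one mean home-exercise-minutes value per participant, keeping p ≤ 0.05.

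The sponsor should also consider stating three choices, which the required change does not depend on but which complete the specification:

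1. Pooled or Welch variance.
2. Two-sided or one-sided testing, since the hypothesis is directional but no sidedness is given.
3. Whether each mean is taken over all 16 scheduled home sessions with missed sessions as zero, or over completed sessions only. The first measures adherence and duration together; the second measures duration when exercising.

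The cost is one phrase, changed before the data are analysed. The timing data are already planned, and no extra participants are needed. Only the missed-as-zero option asks for more: a missed session would have to be distinguishable from an unrecorded one, which the documents do not address.
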